**10.8. Appendix 8: Multiple Comparisons & Multiplicity****10.8.1. Handling of Multiple Comparisons & Multiplicity**

No adjustments for multiplicity will be made.

## 10.9. Appendix 9: Model Checking and Diagnostics for Statistical Analyses

### 10.9.1. Statistical Analysis Assumptions

Endpoint(s)	
 
• PK endpoints AUC and Cmax
 

Analysis	
 
• Mixed Effects
 

 
• Model assumptions will be applied, but appropriate adjustments maybe made based on the data.
 
• The Kenward and Roger method for approximating the denominator degrees of freedom and correcting for bias in the estimated variance-covariance of the fixed effects will be used.
 
• Distributional assumptions underlying the statistical analyses will be assessed by visual inspection of residual plots. Normality will be examined by normal probability plots, while homogeneity of variance will be assessed by plotting the residuals against the predicted values for the model.
 
	

## 10.10. Appendix 10 – Abbreviations & Trade Marks

### 10.10.1. Abbreviations

Abbreviation	Description
ADaM	Analysis Data Model
AE	Adverse Event
Ae	Amount excreted in urine
AUC	Area under the curve
AUC(0-t)	AUC from time zero to the time of last quantifiable concentration
AUC(0-∞)	AUC from time zero to infinity
AUC(0-τ)	AUC over the dosing interval τ
A&R	Analysis and Reporting
CDISC	Clinical Data Interchange Standards Consortium
CI	Confidence Interval
CL	Total systemic clearance
CL r	Renal clearance
C max	Concentration at maximum
C τ	Trough concentration
CPMS	Clinical Pharmacology Modelling & Simulation
CrI	Credible interval
CS	Clinical Statistics
CSR	Clinical Study Report
CTR	Clinical Trial Register
CV b / CV w	Coefficient of Variation (Between) / Coefficient of Variation (Within)
DOB	Date of Birth
DP	Decimal Places
eCRF	Electronic Case Record Form
Feu(t1-t2)	Urinary excretion ratio relative to dose
IA	Interim Analysis
ICH	International Conference on Harmonisation
IDSL	Integrated Data Standards Library
IMMS	International Modules Management System
IP	Investigational Product
GUI	Guidance
MCMC	Markov Chain Monte Carlo
PCI	Potential Clinical Importance
PDMP	Protocol Deviation Management Plan
PK	Pharmacokinetic
PP	Per Protocol
QC	Quality Control
QTcF	Frederica's QT Interval Corrected for Heart Rate
QTcB	Bazett's QT Interval Corrected for Heart Rate
RAP	Reporting & Analysis Plan

Abbreviation	Description
Ratio of accumulation	Accumulation ratio, calculated by AUC(0- $\tau$ ) on day 15/ AUC(0- $\tau$ ) on day 1
Ratio of time invariance	Time invariance ratio, calculated by AUC(0- $\tau$ ) on day 15/ AUC(0- $\infty$ ) on day 1
SAC	Statistical Analysis Complete
SDTM	Study Data Tabulation Model
SOP	Standard Operation Procedure
TA	Therapeutic Area
TFL	Tables, Figures & Listings
t 1/2	Terminal elimination half-life
T max	Time of maximum concentration
V ss	Steady-state volume of distribution
GSK	GlaxoSmithKline

### 10.10.2. Trademarks

Trademarks of the GlaxoSmithKline Group of Companies
NONE

Trademarks not owned by the GlaxoSmithKline Group of Companies
WinNonlin
SAS

## 10.11. Appendix 11: List of Data Displays

### 10.11.1. Data Display Numbering

The following numbering will be applied for RAP generated displays:

Section	Tables	Figures
Study Population	1.1 to 1.9	
Safety	2.1 to 2.17	2.1
Pharmacokinetic	3.1 to 3.22	3.1 to 3.22
Section	Listings	
ICH Listings	1 to 47	

### 10.11.2. Mock Example Shell Referencing

Non IDSL specifications will be referenced as indicated and if required an example mock-up displays provided in the TLF Specification documents.

Section	Figure	Table	Listing
Study Population	POP_Fn	POP_Tn	POP_Ln
Safety	SAFE_Fn	SAFE_Tn	SAFE_Ln
Pharmacokinetic	PK_Fn	PK_Tn	PK_Ln

**NOTES:**

- Non-Standard displays are indicated in the 'IDSL / TST ID / Example Shell' or 'Programming Notes' column as '[Non-Standard] + Reference.'

### 10.11.3. Deliverable [Priority]

Delivery [Priority] 	Description
DE [X]	Dose Escalation
SAC [X]	Final Statistical Analysis Complete

**NOTES:**

- Indicates priority (i.e. order) in which displays will be generated for the reporting effort.

**10.11.4. Study Population Tables**

Study Population Tables					
No.	Population	IDSL / TST ID / Example Shell	Title	Programming Notes	Deliverable [Priority]
Subject Disposition and Analysis Sets					
1.1	Safety	NS	Summary of Number of Subjects Enrolled by Country and Site ID		SAC [1]
1.2	Safety	ES1	Summary of Subject Disposition		SAC [1]
1.3	Screened	ES6	Summary of Reasons for Screening Failures		SAC [1]
1.4	Screened	DV1	Summary of Important Protocol Deviations		SAC [1]
Demographics and Baseline Characteristics					
1.5	Safety	DM1	Summary of Demographic Characteristics		SAC [1]
1.6	Safety	DM11	Summary of Age Ranges		SAC [1]
1.7	Safety	DM5	Summary of Race and Racial Combinations		SAC [1]
1.8	Safety	DM6	Summary of Race and Racial Combinations Details		SAC [1]
Medical Conditions					
1.9	Safety	MH1	Summary of Cardiovascular Related Medical Conditions		SAC [1]

## 10.11.5. Safety Tables

Safety : Tables					
No.	Population	IDSL / TST ID / Example Shell	Title	Programming Notes	Deliverable [Priority]
Adverse Events					
2.1	Safety	AE2	Relationship of Adverse Event System Organ Classes, Preferred Terms and Verbatim Text		SAC [1]
2.2	Safety	AE1	Summary of All Adverse Events		SAC [1]
2.3	Safety	AE1	Summary of Drug-Related Adverse Events		SAC [1]
2.4	Safety	A15	Summary of Common (>=5%) Non-serious Adverse Events by System Organ Class and Preferred Term (Number of Subjects and Occurrences)		SAC [1]
2.5	Safety	A16	Summary of Serious Adverse Events by System Organ Class and Preferred Term (Number of Subjects and Occurrences)		SAC [1]
Laboratory Measurements					
2.6	Safety	LB1	Summary of Clinical Chemistry Values		SAC [1]
2.7	Safety	LB1	Summary of Clinical Chemistry Change from Baseline		SAC [1]
2.8	Safety	LB1	Summary of Haematology Values		SAC [1]
2.9	Safety	LB1	Summary of Haematology Change from Baseline		SAC [1]
2.10	Safety	UR3b	Summary of Urinalysis Dipstick Results		SAC [1]
Electrocardiograms					
2.11	Safety	EG1	Summary of ECG Findings		SAC [1]
2.12	Safety	EG2	Summary of ECG Values		SAC [1]
2.13	Safety	EG2	Summary of Change from Baseline in ECG Values		SAC [1]
2.14	Safety	SAFE_T1	Summary of Frequency of Maximum Post-Dose ECG Parameter Corrected QTc Interval		SAC [1]

Safety : Tables					
No.	Population	IDSL / TST ID / Example Shell	Title	Programming Notes	Deliverable [Priority]
2.15	Safety	SAFE_T2	Summary of Frequency of Maximum Change from Baseline for ECG Parameter Corrected QTc Interval		SAC [1]
Vital Signs					
2.16	Safety	VS1	Summary of Vital Signs		SAC [1]
2.17	Safety	VS1	Summary of Vital Signs Change from Baseline		SAC [1]

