5.4.3. Renal Stopping Criteria

Study treatment will be discontinued for a subject who meets any of the following criteria:

- Persistent (confirmed on recheck) elevation of serum creatinine (>0.3 mg/dL) without an alternative cause identified
- Albumin to creatinine ratio ≥ 0.03 mg/mg
- New blood in urinalysis confirmed by microscopy without an alternative cause identified

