7.3.7. Clinical Safety Laboratory Assessments

All protocol required safety laboratory assessments, as defined in [Table 7](#), must be conducted in accordance with the Laboratory Manual, and Protocol Time and Events Tables (Section [7.1](#)). Laboratory requisition forms must be completed and samples must be clearly labelled with the subject number, protocol number, site/center number, and visit date. Details for the preparation and shipment of samples will be provided by the laboratory and are detailed in the Study Reference Manual (SRM). Reference ranges for all safety parameters will be provided to the site by the laboratory responsible for the assessments.

If additional non-protocol specified laboratory assessments are performed at the institution's local laboratory and result in a change in subject management or are considered clinically significant by the investigator (e.g., SAE or AE or dose modification) the results must be recorded in the eCRF.

Refer to the SRM for appropriate processing and handling of samples to avoid duplicate and/or additional blood draws.

Hematology, clinical chemistry, urinalysis, and additional parameters to be tested are listed in [Table 7](#).

Table 7 Protocol Required Safety Laboratory Assessments

Laboratory Assessments	Parameters			
Hematology	Platelet Count	Total iron ¹	RBC Indices:	WBC count with Differential:
	RBC Count	TIBC ¹	MCV	Neutrophils
	Hemoglobin	Ferritin ¹	MCH	Lymphocytes
	Hematocrit		MCHC	Monocytes
	Reticulocytes ¹			Eosinophils
				Basophils
Additional Iron Tests ²	Transferrin (apotransferrin)		Ceruloplasmin	Haptoglobin/Hemopexin
Clinical Chemistry ³	Blood urea nitrogen	Potassium	AST	Total and direct bilirubin
	Creatinine	Sodium	ALT	Total protein
	Glucose	Calcium	Alkaline phosphatase	Albumin
	Bicarbonate	Chloride	Uric acid	
Urinalysis	
 • Specific gravity • pH, glucose, protein, blood and ketones by dipstick • ACR⁴ • Microscopic examination (if blood or protein is abnormal) • NGAL⁵ • KIM-1⁵ • Urine color⁶ 			

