Other Screening Tests	
 • Human immunodeficiency virus • Hepatitis B surface antigen • Hepatitis C antibody • Follicle-stimulating hormone and estradiol (as appropriate) • Alcohol, cotinine, and drug screen (to include at minimum: amphetamines, barbiturates, cocaine, opiates, cannabinoids and benzodiazepines) • β-human chorionic gonadotropin pregnancy test (if female of child-bearing age; serum at screening and urine at Day -1 and follow-up) 			

ACR = albumin to creatinine ratio, ALT = alanine aminotransferase, AST = aspartate aminotransferase, KIM-1 = kidney injury molecule 1, MCH = mean corpuscular hemoglobin, MCHC = mean corpuscular hemoglobin concentration, MCV = mean corpuscular volume, NGAL = Neutrophil gelatinase-associated lipocalin, RBC = red blood cell, TIBC = total iron binding capacity, WBC = white blood cell
 
Footnotes are on the next page.
				

NOTES:

1. In Parts 1 and 3, analyzed on Day –1 and at Follow-up visit. In Part 2, analyzed on Day –1, Day 5, Day 15, and at Follow-up visit.
2. Blood samples will be collected on Day –1, predose (at least 1 hour before dosing) on Days 5, and 15, and at Follow-up visit..
3. Details of Liver Chemistry Stopping Criteria and Required Actions and Follow-Up Assessments after liver stopping or monitoring event are given in Section 5.4.1, Appendix 2, and Appendix 3.
4. The ACR on urine albumin and creatinine will be determined using the first morning void urine at Screening and Follow-up visit for all subjects in both parts of the study. In addition, the ACR will be determined on Day 2 in Parts 1 and 3, and Days 5 and 15 in Part 2. Screening ACR may be performed on urine during the screening visit. Subjects should be provided a sterile urine transport container and instructions on how to collect a first void urine at home for screening. In the event a subject fails by ACR, the subject should be contacted to bring back first void urine for recheck. For the Follow-up visit, subjects must be provided a sterile urine transport container on discharge from the clinical unit and instructed to bring back the first morning void urine on the day of their return Follow-up visit.
5. An aliquot of the remaining urine samples will be banked and may be analyzed for NGAL and KIM-1 after the end of the study if a clinical signal is detected. Instructions for collection and storage of these urine samples are included in the Study Reference Manual.

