9.4. Key Elements of Analysis Plan

9.4.1. Primary Analyses

Safety Analyses

The following safety evaluations will be performed:

- Monitoring for AEs
- Routine clinical laboratory tests including chemistry, hematology, and urinalysis
- Vital signs
- Twelve-lead ECG readings
- Continuous cardiac monitoring (dual-lead telemetry)

Safety endpoints will include AEs, clinical laboratory test results (chemistry [including liver function parameters], hematology, and urinalysis), vital signs (BP, heart rate, respiratory rate, and body temperature), and 12-lead ECG readings.

All safety data will be presented in data listings. Subject demographics, medical history, and prior and concomitant medications will be summarized for each dose level using descriptive statistics. For continuous variables, these summaries will include number of subjects, mean, median, standard deviation, minimum, and maximum.

For categorical variables, the summaries will include frequencies and corresponding percentages. No inferential hypothesis testing will be performed on the safety variables.

Adverse events will be coded using the MedDRA classification system.

Treatment-emergent AEs will be defined as any AEs, regardless of relationship to study drug, that occur after the dose of study drug until the Follow-up visit. The treatment-emergent AEs will be summarized for each dose level at AE onset for the overall number of AEs and percentage of subjects who experience them. The total number of AEs will be summarized by dose level and overall. The AEs will be further summarized by severity and relationship to the study drug. If relationship information is missing, the AE will be considered treatment related. Listings for the subsets of SAEs

and treatment-related SAEs will be provided. The SAEs and number of AEs leading to discontinuation will be summarized. The incidence of AEs will also be summarized by system organ class and preferred term.

Clinical laboratory test results, vital signs, and 12-lead ECG results will be summarized by actual values and change from baseline. Clinical laboratory values that are outside of the reference ranges will be flagged and evaluated for clinical significance by the investigator. Any 12-lead ECG abnormalities will be summarized by each dose level. Physical examination findings and cardiac telemetry results will be listed.

Detailed descriptions of the analyses in this study will be presented in the RAP.

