**Table 3 Overview of Planned Safety Analyses**

Display Type	Absolute				Change from Baseline			
	Summary		Individual		Summary		Individual	
	T	F	F	L	T	F	F	L
Exposure								
Extent of Exposure	Y			Y				
Adverse Events								
All AEs	Y			Y				
All Drug-Related AEs	Y			Y				
Serious AEs				Y				
Withdrawal AEs				Y				
Laboratory Values								
Clinical Chemistry	Y			Y	Y			
Hematology	Y			Y	Y			
Urinalysis (Dipstick)	Y			Y				
ECGs								
ECG Findings	Y			Y				
ECG Values	Y			Y	Y			
Vital Signs								
Vital Signs	Y			Y	Y			
Cardiac Telemetry								
Cardiac Telemetry				Y				
Liver								
Liver Events [1]				Y				
Cardiovascular								
Cardiovascular Events [1]				Y				
Injection Site Reactions								
Injection Site Reaction Events [1]				Y				
Rash								
Rash Events [1]				Y				
Biomarker								
Cytokines			Y	Y				

---

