**CONFIDENTIAL**

204847

ICH : Listings					
No.	Population	IDSL / TST ID / Example Shell	Title	Programming Notes	Deliverable [Priority]
12	Safety	AE8	Listing of All Adverse Events		SAC [1]
13	Safety	AE8	Listing of Drug-Related Adverse Events		SAC [1]
14	Safety	SAFE_L2	Listing of Serious Adverse Events		SAC [1]
15	Safety	AE8	Listing of Adverse Events Leading to Withdrawal from Study		SAC [1]
16	Safety	SAFE_L3	Listing of Infusion Site Reaction Adverse Events	Conditional display	SAC [1]
17	Safety	SAFE_L4	Listing of Liver Adverse Events	Conditional display	SAC [1]
18	Safety	SAFE_L5	Listing of Cardiovascular Adverse Events	Conditional display	SAC [1]
19	Safety	SAFE_L8	Listing of Rash Events	Conditional display	SAC [1]
Laboratory Measurements					
20	Safety	LB5	Listing of Clinical Chemistry Toxicities of Grade 3 or Higher		SAC [1]
21	Safety	LB5	Listing of All Clinical Chemistry Data for Subjects with Toxicities of Grade 3 or Higher		SAC [1]
22	Safety	LB5	Listing of Haematology Toxicities of Grade 3 or Higher		SAC [1]
23	Safety	LB5	Listing of All Haematology Data for Subjects with Toxicities of Grade 3 or Higher		SAC [1]
24	Safety	UR2a	Listing of Urinalysis Toxicities of Grade 3 or Higher		SAC [1]
25	Safety	UR2a	Listing of Urinalysis Data for Subjects with Toxicities of Grade 3 or Higher		SAC [1]
ECGs					
26	Safety	EG5	Listing of Abnormal ECG Findings		SAC [1]
27	Safety	EG5	Listing of All ECG Findings for Subjects with an Abnormal Finding		SAC [1]
28	Safety	EG3	Listing of ECG Values of Potential Clinical Importance		SAC [1]

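### No SAP table summarises the albumin-to-creatinine ratio (ACR), a renal stopping criterion, and no listing shows it unless the subject also has a Grade 3+ urinalysis toxicity or an SAE

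*SAP*

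**What the plan says.** **Protocol.** Section 5.4.3 lists "Albumin to creatinine ratio ≥ 0.03 mg/mg" among the findings that end study treatment, and the risk table in 4.6.1 repeats the threshold. Table 7 in 7.3.7 places ACR in the urinalysis panel, on a separate line from "pH, glucose, protein, blood and ketones by dipstick". Its notes schedule ACR at Screening and Follow-up for all subjects and add: "In addition, the ACR will be determined on Day 2 in Parts 1 and 3, and Days 5 and 15 in Part 2". Section 9.4.1 names urinalysis among the safety endpoints and states that "All safety data will be presented in data listings". It also requires clinical laboratory results to be summarised by actual value and change from baseline. Section 9.1 promises descriptive comparison with placebo.

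**SAP.** Section 2.1 declares no change to the protocol's analysis. Table 3 plans urinalysis displays for dipstick only, with no change from baseline. The one urinalysis table in 10.11.5 is Table 2.10, "Summary of Urinalysis Dipstick Results". Section 10.11.9 has two urinalysis listings: Listing 24, "Listing of Urinalysis Toxicities of Grade 3 or Higher", and Listing 25, which gives urinalysis data for the subjects who have such a toxicity. The urinalysis grades in 10.7.1 cover proteinuria and hematuria only. The baseline table in 10.3.2.1 has rows for hematology, chemistry, ECG and vital signs, and none for urinalysis. ACR is named in the SAP only in the Time and Events notes carried over from the protocol.

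**The concern.** The protocol can take a subject off drug for an ACR result, yet the SAP plans no display that would reliably show that result. Safety is the primary objective in all three parts, and the kidney is a named risk. Protocol 4.6.1 reports a slight change in urinary albumin at 2000 mg/kg in animals, of unclear relevance. Section 4.5 uses exposures at that animal dose to set the human exposure limits. Protocol Table 9 predicts a median AUC(0-24) of 3078 h•µg/mL at 4000 mg TID, above the NOAEL exposure of 2875. Part 2 may therefore reach the exposure range in which albumin changed in animals. The quantitative urinary albumin marker would then be missing from the dose-versus-placebo comparison in the study report.

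**Working it through.** The plan gives no figure to reproduce. The check has three steps.

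**1. Where could an ACR value appear?**

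| SAP display | Who enters it | Can it show ACR? |
|---|---|---|
| Table 2.10 | all subjects | No: dipstick categories |
| Tables 2.6 to 2.9 | all subjects | Not as specified: chemistry and hematology, whereas ACR is in the urinalysis panel |
| Listing 24 | results of Grade 3 or higher | No: ACR has no grade |
| Listing 25 | subjects with a Grade 3 or higher urinalysis toxicity | Possibly: generic test-and-result layout |
| Listing 14 | SAEs | Possibly: column for relevant assessments |
| Listings 12 and 15 | AEs, and AEs leading to withdrawal | The event if recorded as an AE, with no laboratory result column |
| Table 1.2, Listing 2 | withdrawals | Reason only; Table 1.2 has a stopping-criteria category that does not say which criterion |

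**2. Would reaching the ACR threshold trigger Listing 25 through proteinuria?** Grade 3 proteinuria is 4+ or 2 to 3.5 g/day, and Grade 1 starts at 1+ or 200 mg/day (SAP 10.7.1). The two scales are linked by

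albumin per day = ACR × creatinine excreted per day.

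The documents give no creatinine excretion, so I assume 0.8 to 2.0 g/day and count albumin as the urinary protein.

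| Creatinine (g/day) | Albumin at ACR 0.03 (mg/day) | 200 mg ÷ albumin | 2000 mg ÷ albumin |
|---|---|---|---|
| 0.8 | 24 | 8.3 | 83 |
| 1.0 | 30 | 6.7 | 67 |
| 1.5 | 45 | 4.4 | 44 |
| 2.0 | 60 | 3.3 | 33 |

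The stopping threshold lies 3.3 to 8.3 times below the start of Grade 1 and 33 to 83 times below the start of Grade 3. Conversely, 2 g/day corresponds to an ACR of 2/2.0 = 1.0 to 2/0.8 = 2.5 mg/mg. A subject stopped at or near 0.03 would enter Listing 25 only through a separate Grade 3 or higher urinalysis finding.

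**3. How many values are affected?** Planned enrolment is 48 in Part 1, 30 in Part 2 and 10 in Part 3 (Protocol 4.3).

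- Parts 1 and 3: Day 2 and Follow-up, (48 + 10) × 2 = 116.
- Part 2: Days 5 and 15 and Follow-up, 30 × 3 = 90.
- Total after first dose: 116 + 90 = 206.

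The 88 Screening values (48 + 30 + 10) come before any dose. They matter as baselines but are not part of the 206.

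**The case against.** A sponsor could fairly reply on six points.

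- **ACR is not shut out of every output.** A reader might infer that no display can ever show it. The documents do not support that: Listing 25 is not limited to dipstick tests, and Listing 14 can carry assessments relevant to an SAE.
- **Stopping for ACR does not arise in every part.** Parts 1 and 3 give one infusion on Day 1, and the first post-dose ACR is on Day 2, so no treatment remains to stop. The risk table speaks of pausing Part 1 progression or interrupting Part 2 dosing. The stopped-subject case is confined to Part 2: about 30 subjects, 24 of them on active drug (3 cohorts × 8).
- **Restricted listings are the SAP's general pattern.** Chemistry, hematology, ECG and vital-sign listings are also filtered by grade, abnormality or clinical importance. That is true, but those measures have summary tables of values and changes. ACR has neither a summary nor a full listing.
- **Renal monitoring is not left without displays.** Serum creatinine and blood urea nitrogen fall in Tables 2.6 and 2.7, and dipstick results in Table 2.10. These do not replace a urinary albumin measure.
- **Escalation displays would not change.** The safety tables and listings are final-analysis deliverables; only the Bayesian PK displays are marked for dose escalation. The gap is in reporting. It does not show that subjects would go unmonitored during the trial.
- **Urine colour is a different omission.** It is not a stopping criterion. Amendment 1 added it, whereas the SAP synopsis says the SAP is based on the original protocol, and its Part 2 objective and schedule note lack it. A version mismatch is the likely cause.

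These replies narrow the point but leave the conflict with Protocol 9.4.1 in place.

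**Conclusion.** The concern holds in a bounded form. The SAP has no ACR summary in any part and no listing that shows ACR for all subjects. A Part 2 subject stopped on ACR alone, with no Grade 3 or higher urinalysis toxicity and no SAE, would have no ACR value in the planned outputs. This contradicts both commitments in Protocol 9.4.1, to summarise laboratory results and to list all safety data, while SAP 2.1 declares no departure. It is therefore more than missing detail.

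About 206 planned post-dose values have no assured display. That is a count at approximate planned enrolment, with no claim that every value would be lost. The finding that the ACR threshold would not trigger Listing 25 through proteinuria rests on the assumed creatinine range and on treating albumin as the urinary protein. The gap between 0.03 and Grade 3 is at least 33-fold across that range. The consequence is an incomplete safety report, cheap to repair before database lock.

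**What to change.** Add to SAP 10.11:

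- **A summary of ACR** by visit and dose, including placebo, with actual values and change from baseline.
- **A stated ACR baseline** in 10.3.2.1. ACR is scheduled at Screening and not on Day -1, so use the Screening value that confirmed eligibility. Protocol 7.3.7 lets Screening ACR come from urine passed during the visit, and exclusion criterion 19 allows a second measurement. The SAP's default of averaging replicates could otherwise mix the two. Footnote baselines that were not a first morning void.
- **A count of subjects** at or above the protocol's 0.03 mg/mg, by dose and placebo.
- **An unrestricted ACR listing** with that threshold flagged. It should include confirmatory repeats, which Protocol 5.4 requires and which SAP 10.3.3 would keep out of summary tables if they are recorded as unscheduled.

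Separately, bring the SAP into line with Amendment 1 by listing Day 15 urine colour for Part 2.

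The data are already collected, and no clinical rule or assessment changes. The cost is a few extra displays and one baseline definition.
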